8.3. Safety Visit Compliance

To measure the impact of COVID19 on patients' visits compliance for AEs, physical exams, labs and study drug. The proportion of visits that were missed or late will be graphed over time, by calendar month. Could also have some pre/post-COVID19 subgroup analysis.

8.4. Concomitant Medications

Concomitant medications will be defined as all medications taken by the patient any time on-study (on or after the first infusion date of any of eryaspase or chemotherapy) or within 30 days after the last administration date. Previous medication will be defined as all medications taken by the patient before the first infusion of any of eryaspase or chemotherapy.

In case the date value does not allow allocation of a medication to previous or concomitant category, this medication will be considered as concomitant.

Concomitant and previous medications, not including subsequent anti-cancer therapies, will be summarized using data recorded in the "Previous and concomitant treatments" eCRF pages. Subsequent anti-cancer therapies will also be summarized separately

Concomitant medications will be coded using the WHO Drug dictionary. Results will be tabulated by Anatomic Therapeutic Class (ATC) and Preferred Term.

The use of concomitant medications will be included in by-subject data listing.

Sponsor:	NOPHO – Nordic Society of Pediatric Hematology & Oncology		
Protocol:	NOR-GRASPALL 2016		
Document Version No.:	2.0	Document Date:	14-May-2021

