5.0 STUDY DESIGN

5.1 Study Overview

This is a single arm, multicenter, multinational study to assess the pharmacological activity, safety and immunogenicity of eryaspase in combination with the NOPHO ALL 2008 or ALLTogether pilot protocol chemotherapy protocol administered as second line treatment to children or adult patients from 1 to 45 years old with ALL who experience hypersensitivity reactions (clinical allergic reaction or silent inactivation) to PEG-asparaginase.

[figure not shown]
All patients will receive the NOPHO ALL 2008 or ALLTogether pilot protocol chemotherapy regimen, which consists of an induction treatment, consolidation, delayed intensification phase and maintenance phases, a CNS prophylaxis and interim maintenance for a total of 30 months' treatment duration. Once a patient presents with hypersensitivity to PEG-asparaginase, eryaspase will be given as a replacement therapy for remaining scheduled PEG-asparaginase administrations (Figure 3).

FIGURE 3A. STUDY DIAGRAM – PATIENTS TREATED ACCORDING TO NOPHO ALL 2008:

Erytech internal code GRASPALL 2016-12

FIGURE 4B. STUDY DIAGRAM – PATIENTS TREATED ACCORDING TO ALLTOGETHER PILOT PROTOCOL:

*According to ALLTOGETHER protocol: VLR: 4 doses IR low: 5 doses IR high: 8 doses

Erytech internal code GRASPALL 2016-12

Eryaspase will be administered every 2 weeks for a maximum of 4 doses. Then administered every 6 weeks for 3 doses to the end of planned treatment according to the NOPHO ALL 2008 or ALLTogether pilot protocol.

Assessments include overall safety profile of eryaspase, PK/PD parameters of eryaspase, immunogenicity of eryaspase, during successive courses of treatment with eryaspase.

Primary trial assessments for each patient will continue for 1 month following the end of the planned eryaspase treatment phases (approximately 6 months in case of 7 doses). Each patient will receive cytostatic treatment in about 22 months after last administration of eryaspase according to the NOPHO ALL 2008 or ALLTogether pilot protocol. After cessation of therapy patients will be followed for recurrence of disease or the development of late effects. The follow-up after cessation of therapy should be done according to guidelines on each country and site and includes no assessments for this study. Further details regarding the study assessments during the study are provided in section 9.0.

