5.3 Inclusion Criteria

A patient is eligible for the study if all of the following criteria are met:

1. Male or female aged 1-45 years at diagnosis of ALL
2. First line non-high risk (HR) ALL patients enrolled in NOPHO ALL 2008 or ALLTogether pilot protocol including PEG-asparaginase regimen

3. Documented hypersensitivity reaction to PEG-asparaginase with either:
 - Clinical allergy to PEG-Asparaginase (mild/severe) OR
 - Serum asparaginase activity below the lower level of quantification
4. Karnofsky/Lansky score ≥ 50 .
5. Ability to understand, and willingness to sign, a written informed consent document and to comply with the scheduled visits, treatment plans, laboratory tests, and other study procedures. For patients under 18 years of age, either both parents or the legally appointed representatives will need to provide consent.

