6.4 Prohibited Medications and Treatments

The following medications are prohibited during the study period (from inclusion until 30 days after last administration), and administration will be considered a protocol violation:

- Concomitant vaccination with live vaccines as it may increase the risk of serious infection
- Other L-asparaginase marketed products
- Highly hemolytic agents that may lead to RBCs hemolysis: Acetanilide, Antipyrine Phenazone, and Chloroquin and derivatives

NOTE: Benzodiazepine may be given if indicated.

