- Anemia: Anemia, hemoglobin decreased
- Thrombocytopenia: Thrombocytopenia, platelet count decreased
- Leukopenia: Leukopenia, white blood cells count decreased
- Leukocytosis: Leukocytosis, white blood cells count increased
- Hyperglycemia/Diabetes: Hyperglycemia, Diabetes mellitus, Diabetes mellitus inadequate control, Type 2 diabetes mellitus, blood glucose level increased
- Hypertriglyceridemia: Hypertriglyceridemia, triglycerides increased
- Hepatotoxicity: Liver injury, drug-induced liver injury, hepatocellular injury, Venoocclusive liver disease
- Hyperuricemia: Hyperuricemia, blood uric acid increased
- Hypokalemia: Blood potassium decreased, hypokalemia
- Hyponatremia: Blood sodium decreased, hyponatremia
- Hypocalcemia: Blood calcium decreased, hypocalcemia
- Pancreatitis: Pancreatitis, Acute pancreatitis
- Biochemical pancreatitis: Lipase increased, Amylase increased, pancreatic enzymes increased
- Drug hypersensitivity reaction: Drug hypersensitivity, hypersensitivity, anaphylactic reaction, anaphylactic shock, erythema multiform, edema, dermatitis allergic, face edema
- 4. Other allergic reaction: Rash, Erythema multiform, Food allergy, Anaphylactic shock, Transfusion reactions, Angioedema, allergic transfusion reaction.

All AEs and SAEs will be collected and reported in the patient's eCRF throughout study duration (i.e. for time subject signs the informed consent and until 30 days after last administration of eryaspase or chemotherapy. All AEs along with the coded terms will be listed.

The following general rules apply to adverse events:

Sponsor:	NOPHO – Nordic Society of Pediatric Hematology & Oncology		
Protocol:	NOR-GRASPALL 2016		
Document Version No.:	2.0	Document Date:	14-May-2021

- TEAEs are defined as those AEs that started on or after the first dose of study medication or that worsened after the first dose of study medication and with an onset date occurring during the treatment period.
- Treatment period is defined from the first dosing day of study treatment (minimum of the first dosing day for eryaspase (Day 1) until 30 days after last dose of study treatment (maximum of the last dosing day for eryaspase). This includes the safety follow-up period as well.
- If an AE is reported for a given patient more than once during treatment, the worst severity and the worst relationship to study treatment will be tabulated.

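### SAP 8.4 splits previous from concomitant medication at first eryaspase or chemotherapy, so recorded medicines stopped before eryaspase are tabulated as concomitant or fall in neither category

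*SAP*

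**What the plan says.** Under SAP 8.4 the concomitant category is "all medications taken by the patient any time on-study (on or after the first infusion date of any of eryaspase or chemotherapy". The window closes 30 days past a final dose whose drug is not named. The other category uses the same cut-off: "Previous medication will be defined as all medications taken by the patient before the first infusion of any of eryaspase or chemotherapy". Where dates do not settle the category, "this medication will be considered as concomitant". The tabulation draws on the eCRF pages for previous and concomitant treatments and leaves out only subsequent anti-cancer therapy, which is summarised separately. SAP 5.2.4 also plans a concomitant-treatment table but gives no dates beyond saying that it covers the study.

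Protocol 5.3 admits "First line non-high risk (HR) ALL patients enrolled in NOPHO ALL 2008 or ALLTogether pilot protocol including PEG-asparaginase regimen" and also requires a documented hypersensitivity reaction to PEG-asparaginase. SAP 4.12 describes the preplanned chemotherapy as already in place before inclusion and makes the first day of eryaspase Study Day 1.

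**The concern.** The rule suits a trial in which chemotherapy and study drug start together. Here eryaspase is second line: it replaces the PEG-asparaginase doses that remain after a reaction. The first chemotherapy infusion therefore comes before the first eryaspase infusion, and the eryaspase half of the rule has no effect.

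The table should tell a reader what was given alongside eryaspase. With the SAP's cut-off it would mix that with earlier treatment. If sites recorded them, it could list as concomitant the PEG-asparaginase that qualified the patient for entry and the drugs used to treat that reaction. The first would look like use of a class that Protocol 6.4 prohibits (other marketed L-asparaginase products). The second would blur the background against which hypersensitivity to eryaspase is read.

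**Working it through.** The plan states no figure to reproduce. The check sets the definitions against eligibility and the treatment schedules.

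**1. Which date sets the cut-off.** Cut-off = the earlier of first eryaspase and first chemotherapy infusion. Protocol 5.3 and SAP 4.12 place chemotherapy before entry, so the cut-off is the chemotherapy date.

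**2. Length of the stretch affected.** Days affected = day of first eryaspase − day of first chemotherapy infusion.

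Inputs from the protocol:
- NOPHO ALL 2008: first PEG-asparaginase at day 29 (section 7.4.2), then every two weeks over the early doses (section 1.0), giving days 29, 43, 57 and 71.
- ALLTogether: first dose at day 4 (section 7.4.2), repeated every two weeks (section 1.0), giving days 4, 18 and 32.

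Assumptions: chemotherapy is infused from day 1, and eryaspase takes the place of the next scheduled dose.

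| Backbone | Reaction at dose | First eryaspase, about | Days affected |
|---|---|---|---|
| NOPHO ALL 2008 | 1 (day 29) | day 43 | 43 − 1 = 42 |
| NOPHO ALL 2008 | 2 (day 43) | day 57 | 57 − 1 = 56 |
| NOPHO ALL 2008 | 3 (day 57) | day 71 | 71 − 1 = 70 |
| ALLTogether | 1 (day 4) | day 18 | 18 − 1 = 17 |
| ALLTogether | 2 (day 18) | day 32 | 32 − 1 = 31 |

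Protocol 1.0 reports that 85% of NOPHO ALL 2008 children with allergy reacted after the second or third dose, so 56 and 70 days are the more typical NOPHO values. The documents do not list the infused induction drugs. NOPHO PEG-asparaginase is intramuscular, so it would not itself set the cut-off. In ALLTogether it is intravenous; if it counted as the first chemotherapy infusion, the 17 days would become 18 − 4 = 14.

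**3. What is misallocated.** A medicine started before eryaspase and still running at the first infusion is concomitant under any sensible rule. Those affected are medicines taken after first chemotherapy and stopped before first eryaspase. SAP 8.4 labels them concomitant.

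**4. The narrower reading.** Suppose on-study restricts the concomitant category to the time after enrolment. A medicine stopped before enrolment is then not concomitant. It is not previous either, because that definition has no on-study limit and still ends at first chemotherapy.

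**5. Other anchors in the plan.**
- SAP 4.2: exposure starts with eryaspase.
- SAP 4.12: Study Day 1 is the first day of eryaspase.
- SAP 8.1: "Treatment period is defined from the first dosing day of study treatment", with eryaspase Day 1 named, to 30 days after the last eryaspase dose.
- SAP 8.4: starts at eryaspase or chemotherapy; drug at the end not stated.

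**6. The end of the window.** Read as eryaspase, the last administration gives the same end as the treatment-emergent period. Read as chemotherapy, it runs well past it, since Protocol 5.1 says "Each patient will receive cytostatic treatment in about 22 months after last administration of eryaspase". The text does not choose.

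**The case against.** Several points on the other side carry weight.

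- **The on-study qualifier.** Treatment before enrolment is not ordinarily on-study, so the rule need not sweep PEG-asparaginase into the table. That stands as a possible reading, but it leaves the gap shown in step 4.
- **Dependence on recording.** A reader might infer that all patients would show PEG-asparaginase as concomitant, because all were exposed. The documents do not support that as a certainty. The eCRF pages are not shown. Protocol 9.1 and 9.2 ask for concomitant medications at screening and newly added ones at each dose, and prior asparaginase reactions have their own summary in SAP 5.2.2. The rule acts only on what was entered.
- **Detecting prohibited use.** A reader might infer that another asparaginase given on study could not be told apart from the qualifying PEG-asparaginase. That is true at most of the summary table. SAP 8.4 plans by-subject listings, Protocol 12.7 makes prohibited medication a protocol violation with its own form, and SAP 4.14 requires a final violation file before hard lock. None of these depends on the 8.4 cut-off.
- **The long forward window.** A reader might infer a window running about 22 months past eryaspase. That figure is a duration of treatment, not of data collection. The protocol synopsis gives participation of about 1.5 years with treatment of about 6 months, leaving about 1.5 − 0.5 = 1 year after eryaspase. What stands is the ambiguity.
- **The comparators.** Protocol 6.4 fixes when drugs are "prohibited during the study period (from inclusion until 30 days after last administration"; it does not say how medications are tabulated, so a different window is not a contradiction. SAP 8.1 is not uniformly anchored to eryaspase either: its sentence on adverse-event collection ends 30 days after eryaspase or chemotherapy. Its treatment-emergent period, which drives the tables, is tied to eryaspase.

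**Conclusion.** The definition is wrong for this design. Under one reading of on-study it labels as concomitant medicines that had stopped before eryaspase; under the other it leaves those stopped before enrolment unclassified. No other section repairs it. It also disagrees with the eryaspase anchors used for exposure, Study Day 1 and treatment-emergent events, and its end date names no drug.

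The stretch affected is about 42 to 70 days (NOPHO ALL 2008, reaction at doses 1 to 3) or about 17 days and upwards (ALLTogether), on the assumptions in step 2. The number of patients and medicines affected cannot be given without the eCRF pages.

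The effect is confined to a descriptive safety table. The primary binomial test, the analysis populations, the PK parameters and the treatment-emergent definition do not use this cut-off. It is a modest point, worth correcting because the table would otherwise misdescribe what accompanied eryaspase.

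**What to change.** In SAP 8.4:

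1. Delete the reference to chemotherapy from both definitions.
2. Define previous as stopped before the first eryaspase infusion.
3. Define concomitant as ongoing at, or started on or after, the first eryaspase infusion and up to 30 days after the last eryaspase infusion. This also settles which last administration is meant.
4. Identify prohibited-medication use over the Protocol 6.4 period, from inclusion to 30 days after last administration. The period between inclusion and first eryaspase is then covered, and the PEG-asparaginase that qualified the patient for entry is not counted.
5. Point SAP 5.2.4 to the same definitions.

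A separate table of prior asparaginase is optional.

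The cost is a wording change and one derivation in the programming, plus the Protocol 6.4 window for the prohibited-use check. No new data are needed.

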9. CHANGES TO PLANNED ANALYSES

The primary objectives noted in the protocol was an evaluation of the pharmacological (PK and PD) profile of eryaspase. This evaluation would be based on the PK parameters and the CSF concentration of amino acids. These two endpoints have been moved to secondary endpoints. However, the protocol does note the primary endpoint to include the percentage of patients with continuous ASNase activity >100 U/L, which is consistent with the revised primary endpoint of percentage of patients with ASNase concentration >100 U/L following the first infusion.

Sponsor:	NOPHO – Nordic Society of Pediatric Hematology & Oncology		
Protocol:	NOR-GRASPALL 2016		
Document Version No.:	2.0	Document Date:	14-May-2021

